## METHOD

### Overview

We plan to conduct a multi-site randomized controlled trial of AD-MIL, comparing it to PCT (Frost et al., 2014). Study recruitment and treatment will occur off-site at four VA partnering sites: Minneapolis, MN, San Diego, CA (Oceanside CBOC), San Francisco, CA, and Waco, TX (Center for Returning Veterans Center of Excellence at the Central Texas Veterans Healthcare System; CTVHCS). VA Boston's research roles are to: (1) conduct weekly and PRN oversight and supervision meetings to problem-solve recruitment, treatment delivery, patient compliance, and data collection issues; (2) conduct blinded phone interviews to diagnose PTSD using the Clinician-Administered PTSD Scale for DSM-5 (CAPS-5) before treatment and at three time points after treatment; (3) manage and analyze de-identified data sets; and (4) help prepare manuscripts and reports.

The trial will follow the consensus recommendations for clinical trials in the VA (VA-ORD, 2008): (1) clearly defined target symptoms: Functional and clinical outcomes will be operationalized; (2) reliable and valid measures: Assessment tools are selected for their content relevance and psychometric properties; (3) use of blind evaluators of outcome: The evaluator will be independent and blind to treatment condition. The assessor will remind participants to help maintain their blind; (4) assessor training: The independent evaluator (IE) will be carefully trained to criteria and monitored on an ongoing basis; (5) manualized, replicable, specific treatment programs; (6) unbiased assignment to treatment arms and (7) treatment adherence: Sessions will be recorded, and a random percentage will be used to assess treatment integrity. Adherence to the therapy manuals will be monitored by senior supervisors. We will follow the CONSORT guidelines for randomization and participant tracking.

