### *Sample Size*

Power calculations were based on a two-sided, two-sample t-test to compare the differences in mean change. Effect sizes were selected based on a trial comparing Acceptance and Commitment Therapy with PCT in veterans with mental health diagnoses, using the SDS (Lang et al., 2016), which showed a large effect size for reduction in disability ( $d \approx .60$ ), a change of 1.2 points. Lang et al.'s (2016) follow-up interval was 3 months. These correspond to 3-month changes of 1.2 points assuming a standard deviation for the change of 2.1 points as per Lang and colleagues. These power calculations inflate the variance to account for clustering of scores (sites by therapists), with an  $ICC = .02$ . To partially offset possible losses to follow-up, we will follow the Benjamini-Hochberg testing procedure, which is less conservative than the Bonferroni rule (Benjamini & Hochberg, 1995). Each hypothesis is powered to compare outcome at 3 months. Analyses up to 6-months post-treatment are exploratory. Testing five hypotheses, each with Type I error of  $1\% = 5\%/5$ , then with 93 participants per arm, a two-sample t-test, comparing the difference between the 3-month changes, has 90% power to detect an absolute difference of .50 or larger assuming an effect size of .56. To have 80% power with 93 participants per arm requires an effect size of .50.

Note: In consultation with RR&D, we recalculated the number of participants to power the original trial at .8 (vs. .9) and this resulted in a new target N of 148 (74 per arm).

**COVID-19 Aim:** We used the AD grant's power framework to estimate the N required to test our hypothesis that AD would lead to better functional changes relative to PCT in COVID-19 stressed veterans with PTSD. We used the same parameters for mean change and the SD for change in Sheehan scores from the grant and a revised differential effect size prediction of .8. We reasoned that we would expect a larger differential effect size for this sub-study because AD can not only help veterans whose existing PTSD symptoms and impairments are exacerbated by COVID-19 stressors but also because AD includes change agents that can help reduce distress and impairment associated with the day to day demands and stressors of living in the time of COVID-19 (mindfulness, loving kindness meditation, letter-writing, behavioral assignments). With these parameters, we need 74 veterans (37 per arm) to power the aim (at a power of 0.90; one-tailed).

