#### *Treatment Training, Supervision, and Fidelity Monitoring*

Therapists with Ph.D.s in clinical or counseling psychology and VA internship experiences treating veterans with PTSD will be trained to deliver AD-MIL or PCT (not both).

Training and supervision of AD-MIL and PCT trial cases will be provided by Drs. [name] and [name]. [name] developed AD for the Marine Corps trial and has spearheaded the extension of AD principles in the development of AD-MIL. [name] has extensive expertise in the conduct of PCT. Training will involve a review of the respective manuals and supporting materials, intensive supervision of trial cases, and weekly group and one-on-one phone supervision with [name] for AD-MIL and [name] for PCT). Drs. [name] and [name] will review audio recording of treatment sessions (all treatment session will be audiotaped) as needed to facilitate their supervisory roles. Selected sessions will be securely transferred to an approved and secure drive within the VA firewall to Drs. [name] and [name].

Treatment fidelity monitoring will be conducted by Drs. [name] and [name]. [name] was instrumental in the development of AD for the Marine Corps trial and has served as a consultant in the extension of AD principles in the development of AD-MIL. [name] has extensive expertise in the conduct of PCT. Fidelity monitoring will be executed via the following procedure: 100% of a patient's first two sessions will be selected for review, 50% of next two, 20% of next five and 10% thereafter. After ten subjects, the therapist will discuss with the site RA which sessions to send for review to total 10% of caseload. Selected sessions will be securely transferred to an approved and secure drive within the VA firewall to [name]. Selected sessions will be securely transferred to [name] via encrypted email (see attached Data Use Agreement).

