### **ANALYSES**

**Inferential analyses.** The longitudinal and clustered nature of the design produces a multilevel or nested data structure (Raudenbush & Bryk, 2002), with a likelihood of between-subject variability in treatment trajectory over time (e.g. random slopes). In this study, veterans and therapists are nested (clustered) within performance sites. The lower level (level-1) data consists of the repeated measures for each individual at each assessment. Level-1 data is nested within upper level (level-2) person-level variables (e.g., study site).

Using the most up to date statistical software such as SAS 9.4 and R/R Studio, we will explore the change trajectory of endpoints over the course of pre-treatment, during-treatment, and post-treatment time intervals. Specifically, we will use the linear mixed model regression framework to assess the differential treatment effects of endpoint symptom burden over time. We will examine observed measurement scores and specify linear mixed models that best fit the time-change trends (e.g. linear, piecewise). We will test for the presence of random variation, such as between-site cluster effects and between-subject random slopes of treatment effect. We will determine the best fit linear mixed effects model as a combination of most appropriate representation of time and empirically-evidenced random and fixed effects.

The linear mixed effects models will incorporate clinically relevant time-invariant and time-varying predictors and will use Maximum Likelihood Estimation to produce estimates that are unbiased in the presence of random missingness and dropout. They will provide an Intent-To-Treat (ITT) analysis that will incorporate all available data. Per-protocol and “completer” subset analyses will be performed under the same paradigm. Additionally, a subset of subjects whom began therapy during the COVID-19 pandemic will be identified and analyzed separately; they comprise subjects which began therapy following December 31st, 2020. The tenability of the “At-Random” missingness assumption will be assessed and a sensitivity analysis of the results will be conducted to determine robustness of the inferences.

**Aim I:** Randomized controlled trial of AD-E, comparing it to PCT:

**Hypotheses 1 and 2:** Veterans in the AD-E arm will have a steeper downward slope in SDS (primary endpoint). Identical calculations will be performed with the B-IPF and DRRI-2 Post-Deployment Social Support measure.

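### The treatment contrast carries therapist variance, but the mixed models are fitted by ML with no prespecified therapist effect and no degrees-of-freedom method, so the test can be liberal if therapists are few

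*Combined protocol and SAP*

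**What the plan says.** The ANALYSES section says the linear mixed models "will use Maximum Likelihood Estimation to produce estimates that are unbiased in the presence of random missingness and dropout". It recognises that "veterans and therapists are nested (clustered) within performance sites". On random effects it says: "We will test for the presence of random variation, such as between-site cluster effects and between-subject random slopes of treatment effect". The final model is to combine the "most appropriate representation of time and empirically-evidenced random and fixed effects". A therapist random effect is not among the examples. REML, a degrees-of-freedom method and a reference distribution for the test are not mentioned. The same model structure is used for the other continuous outcomes.

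Treatment Training, Supervision, and Fidelity Monitoring says that therapists "will be trained to deliver AD-MIL or PCT (not both", so therapist is nested in arm. Sample Size says that the power calculations "inflate the variance to account for clustering of scores (sites by therapists", with an ICC of .02. It also fixes the per-hypothesis level: "Testing five hypotheses, each with Type I error of" 1%. The number of therapists is not given in any section.

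**The concern.** When each therapist works in one arm only, differences between therapists do not cancel out of the treatment comparison. They add to its error, and the precision of that comparison is governed by the number of therapists as well as the number of veterans. Three features of the plan bear on whether the standard error reflects this.

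- The therapist effect may never enter the model. It is not named, and an effect that must show itself in the data will often be dropped when the ICC is small and therapists are few.
- If it does enter, ML divides the between-therapist sum of squares by the number of therapists and makes no allowance for the fixed effects estimated. REML does make that allowance.
- With no degrees-of-freedom method stated, a large-sample reference could be used although the relevant information comes from a limited number of therapists.

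At stake is the type I error of the primary SDS comparison and of the other outcomes analysed by mixed model. The reason given for ML, validity under random missingness, does not favour ML over REML, because both are likelihood methods using all available data under the same assumption.

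**Working it through.** **The plan's own figures.** The documents state no type I error for the mixed model, only power for a two-sample t-test. With power = Φ(d√(n/2) − 2.576) at two-sided 1%:

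- 93 per arm, d = .56: 3.819 − 2.576 = 1.243, power 0.893 (stated 90%).
- 93 per arm, d = .50: 3.410 − 2.576 = 0.834, power 0.798 (stated 80%).
- 74 per arm, d = .56: 3.406 − 2.576 = 0.830, power 0.797 (stated 80%).

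They reproduce with no further inflation for the ICC, so that allowance is either already inside .56 or was not applied.

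**Inputs for the size of the test.**

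- From the documents: therapist nested in arm; ICC ρ = .02; 74 per arm; ML.
- Assumed, because not given: J = 4, 6 or 8 therapists per arm, with J = 24 for contrast; a normal reference for the test; a balanced design with one change score per veteran; 72 per arm, the nearest size to 74 that divides evenly, so m = 18, 12, 9 and 3 veterans per therapist.

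**Formulas.** Let λ = σ²[1 + (m − 1)ρ]. The variance of the difference in arm means is 2λ/(Jm). ML estimates λ by SSB/(2J) and REML by SSB/(2J − 2), where SSB is the between-therapist sum of squares. Each is pooled with the within-therapist sum of squares when the estimated therapist variance would be negative. Before that pooling, the ML estimate is (2J − 2)/(2J) of the REML estimate: 0.75, 0.83 and 0.875 for J = 4, 6 and 8, and 0.96 for J = 24.

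**Results.** Two-sided size under no treatment effect, ρ = .02, normal reference, 400,000 simulated trials per setting:

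| Therapists per arm | ML, nominal 5% | REML, nominal 5% | Therapist effect omitted, nominal 5% | ML, nominal 1% |
|---|---|---|---|---|
| 4 | 7.5% | 5.9% | 9.2% | 2.2% |
| 6 | 6.4% | 5.4% | 7.9% | 1.7% |
| 8 | 5.9% | 5.1% | 7.1% | 1.4% |

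ML to REML removes 7.5 − 5.9 = 1.6, 6.4 − 5.4 = 1.0 and 5.9 − 5.1 = 0.8 points. At 24 per arm ML gives 5.1%. At ρ = 0 it gives about 4.7%, which is not liberal.

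**Hand check of the omitted-effect column.** The design effect 1 + (m − 1)(.02) is 1.34, 1.22 and 1.16. The effective critical value 1.96/√(design effect) is 1.693, 1.775 and 1.820, giving two-sided sizes of 9.0%, 7.6% and 6.9%. The simulated values are slightly higher because the variance is also estimated.

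**Sensitivity.**

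- At ρ = .05, which the documents do not give, ML gives 10.4%, 8.2% and 7.2% at nominal 5%.
- REML with between-therapist degrees of freedom gives 2.1% to 4.1% over ρ = .02 and .05, so never above nominal.
- A second model adds four random sites (variance share .02) with 1, 2, 3 or 6 therapists per arm per site. At ρ = .02, ML gives 8.0%, 6.0%, 5.5% and 5.1%; REML gives 6.8%, 5.4%, 5.1% and 4.9%; omitting the therapist effect gives 9.4%, 7.2%, 6.4% and 5.6%.
- In that model, with one therapist per arm per site, raising the site variance share from 0 to .10 lowers the ML size from 8.4% to 7.6%.

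**The case against.** Four stronger readings are tempting, and the documents do not support them.

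*There are few therapists.* The documents never say so, and the result turns on it. One indirect clue points the other way. The planning effect is 1.2/2.1 = 0.5714 against the .56 used, and (0.5714/.56)² = 1.041. If that is the clustering allowance at ICC .02, then 1 + (m − 1)(.02) = 1.041 gives m ≈ 3.06 veterans per cluster, or about 74/3.06 ≈ 24 therapists per arm, where ML is harmless. This is only an inference, since the plan does not explain .56.

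*The four sites are the problem.* The plan does state "Study recruitment and treatment will occur off-site at four VA partnering sites", but both arms appear to run at each site, so treatment is compared within sites and a site intercept largely cancels. Sites would matter through a random site-by-treatment effect, which the plan does not clearly specify.

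*ML is the main cause.* It is only part. With the reference distribution held fixed, moving to REML recovers at most 1.6 points in these settings. Omitting the therapist effect does more damage than ML. In the model with sites, ML with a t reference on between-therapist degrees of freedom is conservative (0.6% to 4.5%) at ICC .02. The plan does not say which reference it will use.

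*Every outcome is affected.* The PTSD caseness comparison and the clinical-significance classes are tested by chi-square, so the choice of ML does not touch them.

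It is also fair to say that the simulation uses one change score, whereas the plan compares slopes over repeated measures. The mechanism carries over. The exact percentages may not.

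What stands is that the plan anticipates therapist clustering, nests therapist in arm, and then leaves open whether and how the analysis will allow for it.

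**Conclusion.** The point holds conditionally. The plan does not guarantee that therapist variance enters the standard error of the treatment effect, and the method it names, with no small-sample correction, can understate that variance.

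The excess error needs three things together: non-zero therapist variance, few therapists, and either a large-sample reference or an omitted therapist effect. With 4 to 8 therapists per arm and the plan's ICC of .02, size is about 7.5% to 5.9% at nominal 5% (2.2% to 1.4% at nominal 1%) under ML with a therapist effect, and about 9.2% to 7.1% at nominal 5% without one. With about 24 per arm, or no therapist variance, ML is near nominal. These figures rest on assumed therapist numbers, a balanced design and a single change score.

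This is an improvement that should be made because it is easy to specify. It does not show that the planned test is invalid.

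**What to change.** In the ANALYSES section:

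1. Prespecify a therapist random effect, nested in site and arm, and keep it whatever its own test shows. It must act on the treatment contrast. Because that contrast is a difference in slopes, the effect has to apply to change over time; a therapist intercept alone would not be enough.
2. Fit the final models for the continuous outcomes by REML with Kenward-Roger or Satterthwaite degrees of freedom. Use ML only to compare fixed-effect structures. Validity under missing at random is unchanged.
3. State the planned number of therapists per arm and site, so that readers can judge how much this matters.

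The wording change is small and SAS and R both support it. The statistical cost is wider intervals and some loss of power. With many therapists it is modest. With 4 per arm and 2J − 2 = 6 degrees of freedom, the 5% critical value is 2.447 against 1.960, so intervals are up to about 25% wider (2.447/1.960 = 1.25). At the 1% level the ratio is 3.707/2.576 = 1.44. Fitting site terms with one therapist per arm per site would leave only 3 between-therapist degrees of freedom and could cost more. The test may also be conservative when therapist variance is near zero. The chi-square analyses are not changed by this fix.

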#### **A: Functional and behavioral change hypotheses:**

- A.1.** Immediately post-treatment, 3-, and 6-months post-treatment, veterans with PTSD randomized to AD-MIL will have greater reductions in social, educational, and occupational disability
- A.2.** COVID-19 aim. In the extended time period for the trial, at the post-treatment, or post-treatment and 3-months post-treatment intervals (depending on when the participant was randomized), veterans with PTSD randomized to AD-MIL will have greater reductions in social, educational and occupational disability

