### Participants

Participants will comprise a sample of 148 veterans (including women and members of diverse ethnic and racial groups) with PTSD as a result of military trauma.

To power the COVID-19 aim, we require 74 veterans (including women and members of diverse ethnic and racial groups) with PTSD as a result of military trauma.

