#### *Follow-Up Assessments*

Follow-up assessments will be completed 3 months, 6 months, and 9 months after the first treatment session, or, if no treatment sessions were attended or a participant terminated therapy early, 3 months, 6 months and 9 months after the baseline assessment. As part of these follow-up assessments, all participants will complete CAPS-5 assessments by phone with an IE. In most instances, these calls will occur while the participant is in person at their local VA (i.e., Minneapolis, San Diego, San Francisco, or Central Texas). In cases where a participant is unable to attend a follow-up assessment at their local VA in person, we will offer participants the opportunity to complete the CAPS-5 assessment by phone from their home or another non-VA location. In instances where the participant is not at their local VA, IEs will conduct a thorough risk assessment during the call, and follow thoroughly defined procedures for risk management and safety planning when indicated (see “Follow-up Risk Assessment Phone Script” attached).

**COVID-19 aim:** Participants randomized between 12/31/2020 and 5/31/2021 will complete follow-up assessments 3 months and 6 months after the first treatment session, or, if no treatment sessions were attended or a participant terminated therapy early, 3 months and 6 months after the baseline assessment. Participants randomized between 6/1/2020 and 8/31/2021 will complete a follow-up assessment 3 months after the first treatment session, or, if no treatment sessions were attended or a participant terminated therapy early, 3 months after the baseline assessment.

**COVID-19 Changes:** All communication with participants is being conducted either via a HIPAA-compliant videoconferencing platform or over the phone.

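### The only stated COVID-19 analysis set is limited to veterans who started therapy, while hypothesis A.2 and its follow-up schedule are framed by randomisation

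*Combined protocol and SAP*

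**What the plan says.** Three parts of the combined protocol and SAP bear on who belongs in the COVID-19 comparison.

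- **Analyses (Inferential analyses).** After an intention-to-treat statement for the mixed models and a mention of per-protocol and completer subsets, the text adds that "a subset of subjects whom began therapy during the COVID-19 pandemic will be identified and analyzed separately". Membership is then defined: "they comprise subjects which began therapy following December 31" 2020. No end date is given, and the subset is not linked to a hypothesis.
- **Objectives, functional hypotheses.** A.1 reads "veterans with PTSD randomized to AD-MIL will have greater reductions in social, educational, and occupational disability". A.2, the COVID-19 aim, repeats that claim with only a comma changed. It makes the assessment intervals depend on when the veteran was randomised.
- **Follow-Up Assessments, COVID-19 aim.** Follow-up is assigned by randomisation date. Veterans who never started are still assessed: "if no treatment sessions were attended or a participant terminated therapy early, 3 months and 6 months after the baseline assessment". The second window has the same provision at 3 months.

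The aim has its own sample size. Participants states "To power the COVID-19 aim, we require 74 veterans", and Sample Size states "we need 74 veterans (37 per arm) to power the aim (at a power of 0.90; one-tailed"), with an effect size of .8. No alpha and no non-start rate are given for this aim.

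**The concern.** Randomisation makes the two arms comparable at the moment of assignment. A set chosen by whether the veteran then attended a first session keeps that comparability only if starting is unrelated to arm, or unrelated to outcome. The plan addresses neither condition. It also does not say whether veterans know their assigned therapy before the first session.

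Two veterans randomised on the same day, with the same scheduled assessments, would be treated differently: one analysed and the other dropped, because of something that happened after assignment. The outcomes of the dropped veteran are scheduled for collection and then left out of the only COVID-19 set the plan defines. What is at stake is the validity of A.2 as a comparison of randomised arms.

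**Working it through.** **1. Membership by each section**

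| Veteran | A.2 (Objectives) | Follow-Up Assessments | COVID-19 subset (Analyses) |
|---|---|---|---|
| Randomised in the COVID-19 period, starts therapy after 31 December 2020 | in | assessed, timed from first session | in |
| Randomised in the COVID-19 period, attends no session | in | assessed, timed from baseline | out |

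The sections disagree on the second row.

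**2. What leaving out non-starters can do.** In arm *a*, let q_a be the non-start proportion and k_a the amount (in SD) by which non-starters do worse than starters. The all-randomised mean differs from the starters-only mean by q_a·k_a, so the two contrasts differ by

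shift = q_A·k_A − q_P·k_P (A = AD-MIL, P = PCT).

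No q or k is in the documents. Assumed values show the behaviour:

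- equal q and equal k: shift 0;
- q 15% v 5%, k = 0.25 to 0.5 in both arms: 0.10 × 0.25 = 0.025 to 0.10 × 0.5 = 0.05 SD;
- q 20% v 5%, same k: 0.15 × 0.25 = 0.0375 to 0.15 × 0.5 = 0.075 SD;
- q 20% in both arms, k differing between arms by 0.5: 0.20 × 0.5 = 0.10 SD.

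The last line shows that equal non-start rates do not guarantee a zero shift. The examples illustrate and set no limit. The sign depends on which arm has the larger product.

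**3. How many veterans.** If the 74 are counted at randomisation, non-start of 5%, 10% or 20% (assumed) removes 74 × 0.05 = 3.7, 74 × 0.10 = 7.4 or 74 × 0.20 = 14.8, so about 4 to 15.

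**4. The plan's own power figure.** With d = .8 and 90% power, a one-sided two-sample t-test without clustering needs 28, 34 or 43 per arm at alpha .05, .025 or .01. With 37 per arm, power is 0.96, 0.92 or 0.85. The stated 37 per arm cannot be recovered uniquely, because alpha is missing. One combination that reaches it is alpha .025 with a design effect of 1 + (5 − 1)(.02) = 1.08, giving 34 × 1.08 = 36.7, but the cluster size of 5 is an assumption. The point here does not depend on this figure.

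**5. Power cost of including non-starters.** Assume the same non-start rate q in both arms, d = .8 in starters, no effect in non-starters and no clustering. Power comes from the noncentral t with 2n − 2 degrees of freedom.

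- All randomised: n = 37 per arm, effect .8(1 − q), noncentrality .8(1 − q)·√(37/2). This is 3.097 at q = .10 and 2.753 at q = .20.
- Starters only: n = 37(1 − q) per arm, effect .8, noncentrality .8·√(37(1 − q)/2). This is 3.264 and 3.078.

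| One-sided alpha (assumed) | q = 10%: all v starters | q = 20%: all v starters |
|---|---|---|
| .05 | 0.92 v 0.94 | 0.86 v 0.92 |
| .025 | 0.86 v 0.90 | 0.78 v 0.86 |
| .01 | 0.76 v 0.81 | 0.65 v 0.75 |

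The main power framework states "These power calculations inflate the variance to account for clustering of scores (sites by therapists"), and therapists "will be trained to deliver AD-MIL or PCT (not both"), so therapist effects do not cancel between arms. Allowing for them would lower both figures in each pair, by an amount that depends on caseloads the plan does not give.

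**6. The dates.** The first window runs from 12/31/2020 to 5/31/2021 and the second, as printed, from 6/1/2020 to 8/31/2021. Every date in the first window also lies in the second, and the two assign different follow-up. A set defined by randomisation date therefore has no unambiguous window until these are reconciled.

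**The case against.** The strongest reply is that the subset may not be the test of A.2. The sentence follows the per-protocol and completer subsets and could be one more supplementary analysis. The start of therapy may be only a loose marker for the pandemic period, since follow-up is also dated from the first session. The same paragraph promises an intention-to-treat analysis of all available data.

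Part of this stands. The link to A.2 is an inference. The heading for Hypotheses 1 and 2 in Analyses could be read as covering A.1 and A.2, although Measures attaches A.2 to other functional scales and puts the COVID-19 questionnaire under an A.3 that Objectives does not list. On that reading, however, no COVID-19 population is stated for a separately sized aim, and the wording still needs repair. The general intention-to-treat sentence does not settle the matter, because an analysis of everyone in a set cannot restore people whom the set's definition excludes.

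It is also fair that no consequence has been shown. All the shifts above are assumed, and the standard error of the contrast at 37 per arm is √(2/37) = 0.23 SD, larger than any of them.

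Three stronger readings are not supported:

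- **That a starters-only analysis is passed off as intention-to-treat.** The plan does not give this subset that label.
- **That the rule favours AD-MIL.** Nothing in the documents gives the direction, or shows that there is any bias.
- **That veterans randomised before the cut-off enter by starting late.** Consent and Pre-Eligibility Screening foresees waits between baseline and therapy, but the timing of randomisation is not given, so this is possible rather than shown.

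**Conclusion.** The mismatch is real and worth correcting. The only COVID-19 analysis set in the plan is selected on a post-randomisation event, while A.2 and the COVID-19 follow-up schedule are framed by randomisation and include veterans who never start. If the set is used for A.2, a separately sized comparison of arms loses assessed, randomised veterans. The resulting bias has unknown size and sign and may be zero. It cannot be capped from the documents, because they give no non-start rates and no outcomes for non-starters. The main-trial intention-to-treat analysis is not touched. The case for change rests on validity and not on power, which would fall under the assumptions used here.

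**What to change.** In Analyses, define the COVID-19 set as all veterans randomised within a stated window, with start and end dates, analysed in the arm assigned whether or not they began therapy. State that this set tests A.2. Keep the began-therapy set as a sensitivity analysis, and report the number of non-starters by arm. In Follow-Up Assessments, reconcile the two randomisation windows so that they do not overlap, and use the same dates in Analyses.

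These are wording changes. They need no new assessments, because follow-up of non-starters is already scheduled. The cost is power if non-starters show no treatment effect. Under the assumptions above, the loss is about 0.02 to 0.05 at 10% non-start and about 0.06 to 0.10 at 20%, across one-sided alpha from .05 to .01. Stating the alpha and an expected non-start rate for this aim would let the sponsor replace that range with one figure.

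### The primary SDS slope is not tied to the powered 3-month comparison and its time shape is chosen by fit, so the stated 80% power is not shown to belong to the primary test

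*Combined protocol and SAP*

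**What the plan says.** Sample Size bases power on a two-sided, two-sample t-test of mean SDS change over 3 months: 1.2 points, SD of change 2.1, type I error 1% per hypothesis. A note resets power from .9 to .8, giving 148 participants (74 per arm). On timing it says: "Each hypothesis is powered to compare outcome at 3 months. Analyses up to 6-months post-treatment are exploratory".

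ANALYSES, under Hypotheses 1 and 2, states the primary test as "Veterans in the AD-E arm will have a steeper downward slope in SDS (primary endpoint" (AD-E is that section's name for the experimental arm). The period covered is broad: "we will explore the change trajectory of endpoints over the course of pre-treatment, during-treatment, and post-treatment time intervals". The form of the model is left to the data. The team will look at observed scores and "specify linear mixed models that best fit the time-change trends", with linear and piecewise given as examples. The final model is then to pair whichever coding of time suits best with those effects, random or fixed, that the data support. The same section expects subjects to differ in slope: "with a likelihood of between-subject variability in treatment trajectory over time (e.g. random slopes".

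Follow-Up Assessments schedules visits 3, 6 and 9 months after the first session, and Treatment Arms gives 12 weekly sessions. The three visits therefore fall at about end of treatment, 3 months post-treatment and 6 months post-treatment, which agrees with hypothesis A.1. Under the COVID-19 aim, some participants are scheduled only to month 6 or only to month 3.

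**The concern.** The only power figure for the main trial describes a change between two time points. The primary hypothesis is about a slope, and ANALYSES does not say over what interval, or which segment counts if a piecewise shape is chosen. Nothing in that section carries over the 3-month time point from Sample Size.

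This matters because a single slope over all visits and an early segment answer different questions. One rewards a benefit that keeps growing, and the other rewards an early gain whether or not it lasts. If fit decides between them, the data decide which hypothesis is tested, and the candidates can differ widely in power for the same true effect. The models for Hypotheses 3-6 are to be built the same way, so the ambiguity carries over to them.

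There is also a timing ambiguity. The 3 months in Sample Size could mean the visit 3 months after the first session (about end of treatment) or 3 months post-treatment (about month 6).

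**Working it through.** **1. The plan's own figure.** Inputs from Sample Size: difference 1.2, SD of change 2.1, n = 74 per arm, two-sided alpha .01.

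- d = 1.2/2.1 = 0.571.
- Noncentrality = 0.571 × √(74/2) = 3.476; df = 146; critical t = 2.610.
- Power = 0.805.

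The same inputs with 93 per arm give 0.901. Both stated figures therefore reproduce as the power of a t-test on 3-month change. No clustering inflation enters here. The plan cites an ICC of .02 but gives no cluster size, so I leave clustering out of every figure below to keep the comparisons on one footing.

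**2. Assumptions for the slope.** The documents give no trajectory or covariance, so these are mine: SDS at months 0, 3, 6 and 9; complete data; 74 per arm; alpha .01; a 1.2-point difference at month 3; variance of the 0-to-3-month change held at 2.1² = 4.41. Let f be the share of that variance due to random slopes:

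- Slope variance τ² = f × 4.41/9, residual variance σ² = (1 − f) × 4.41/2, so that 9τ² + 2σ² = 4.41.
- Per-person variance of a linear slope = τ² + σ²/45, because Σ(t − 4.5)² = 45.
- For f = 0, .10 and .25 this is 0.0490, 0.0931 and 0.1593.
- Slope effect per month = Σ(t − 4.5)·m(t)/45, where m(t) is the arm difference at month t.

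Slope effects for differences at months 3/6/9:

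- Held, 1.2/1.2/1.2: (−1.5 + 1.5 + 4.5) × 1.2/45 = 0.120.
- Fading, 1.2/0.9/0.6: (−1.8 + 1.35 + 2.7)/45 = 0.050.
- Growing, 1.2/2.4/3.6: 0.400.

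Worked example, held, f = 0: SE = √(2 × 0.0490/74) = 0.0364; 0.120/0.0364 = 3.30; power 0.753.

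For a piecewise model with a knot at month 3, the first-segment effect is 0.40 per month in all three trajectories. Its generalised-least-squares variance is 0.4492, 0.4532 and 0.4594 for the three values of f.

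| Contrast | f = 0 | f = .10 | f = .25 |
|---|---|---|---|
| Change from baseline to month 3 | 0.805 | 0.805 | 0.805 |
| First segment, knot at month 3 | 0.845 | 0.841 | 0.835 |
| Linear 0-9, held | 0.753 | 0.417 | 0.221 |
| Linear 0-9, fading | 0.112 | 0.056 | 0.035 |
| Linear 0-9, growing | >0.99 | >0.99 | >0.99 |

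A slope fitted only to baseline and month 3 is the change divided by 3, so its power is also 0.805.

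**3. Type I error from choosing the shape.** A null simulation used 20,000 replicates for each of four assumed common trends, without random slopes. It tested the arm difference in the linear slope or first segment, whichever shape was selected.

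| Selection rule | Error at nominal 5% | Error at nominal 1% |
|---|---|---|
| AIC, models with arm-by-time terms | 5.0-8.4% | 1.1-1.9% |
| BIC, models with arm-by-time terms | 5.0-6.0% | 1.1-1.3% |
| Arm-pooled data, AIC or BIC | 4.9-5.1% | 1.0-1.1% |

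**The case against.** The strongest reply is that the two sections can be read together. Sample Size fixes 3 months as the powered time and calls later analyses exploratory, and ANALYSES allows a piecewise model. A baseline-to-3-month slope or first segment is then a permitted primary test, with power of about 80-85%. This stands. A reader might infer that the 80% is wrong or that the trial is underpowered, and the documents support neither. A benefit that goes on growing would put a linear slope above 0.99. What remains is that ANALYSES never says the slope is that segment. Sizing a mixed-model trial with a t-test is common and is not itself a fault.

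The lower power figures rest on assumed trajectories and random-slope shares. They show sensitivity, not a loss in this trial.

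A reader might also infer that choosing the shape by fit materially inflates type I error. That appears mainly under one assumed rule, AIC on models with arm-by-time terms. The plan names no rule, so this is a minor point.

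Nor do the documents suggest that the COVID-19 subset is left out of the primary analysis. The plan says "They will provide an Intent-To-Treat (ITT) analysis that will incorporate all available data" and then "Additionally, a subset of subjects whom began therapy during the COVID-19 pandemic will be identified and analyzed separately", which reads as a further analysis rather than an exclusion. The shortened schedule depends on randomization date, and likelihood methods accept unequal follow-up. A question remains only if the primary contrast sits at a visit some participants were never scheduled to attend.

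Finally, insisting on a fixed visit instead of a pre-specified slope is partly a preference. Either one cures the mismatch.

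**Conclusion.** The point holds in this form: the primary slope is neither pre-specified nor tied to the powered 3-month time point, so the stated 80% has not been shown to be its power. The true figure could be close to 80%, well below it or well above it. The plan does not define the test closely enough to say which. The scenario range, from about 0.04 to above 0.99 for a linear slope over 0-9 months, depends on assumed trajectories, assumed random-slope shares, complete data, no clustering, and reading the 3 months as month 3 after the first session. The mismatch itself needs none of these assumptions and follows from the two sections as written. It should be fixed because it concerns the primary endpoint and the model is to be chosen after outcome scores are seen.

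**What to change.** Before outcome data are examined:

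- State whether the 3 months in Sample Size counts from the first session or from end of treatment.
- Name one primary SDS contrast tied to that time. One option is the arm difference in change from baseline to that visit, from a mixed model with categorical visit and arm-by-visit terms. Another is a pre-specified baseline-to-3-month slope or first segment.
- Fix the time coding, covariates and covariance structure in advance.
- Label the fit-selected linear and piecewise trajectory models secondary or exploratory.
- Restate power for the named contrast, with the clustering allowance and expected dropout shown.
- If the later visit is chosen, say how participants never scheduled for it under the COVID-19 aim are handled.

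The cost is SAP wording and a restated power figure, with no new visits or data. The downside is that a single early contrast is less sensitive to a benefit that emerges only later. If the difference built as 0.4/0.8/1.2 at months 3/6/9 (assumed, and smaller at month 3 than the plan's design effect), the month-3 contrast would have power 0.08. The linear slope would have 0.85 without random slopes, and 0.52 or 0.29 with them at 10% or 25%.
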